10.6.2 Clinical Laboratory

For laboratory measurements, raw values and change from baseline values for the continuous hematology and chemistry results will be summarized in SI units at each visit of the TE Period.

Laboratory tests done in the local laboratory may be used in data analyses if data from the central laboratory are not available.

For hematology and chemistry, the number and percentage of subjects with abnormally low (< lower limit of normal [LLN]) values and with abnormally high (> upper limit of normal [ULN]) values at each visit will be summarized.

The number and percentage of subjects meeting the threshold analysis criterion during the TE Period of the TE Period will be summarized for selected laboratory parameters based on the Safety Set. The threshold analysis criteria are provided in Appendix.

In addition, listings containing individual subject hematology and chemistry values outside of the normal reference ranges will be provided. These listings will include data from both scheduled and unscheduled visits.

LFT elevations meeting ALT or AST > 5xULN, or ALT > 3xULN and total bilirubin > 2xULN, or AST > 3xULN and total bilirubin > 2xULN at one visit during the TE period will also be listed.

10.6.3 Electrocardiogram

For ECG measurements, raw values and change from baseline values will be summarized at each visit of the TE Period for the following standard digital ECG measurements: RR (ms), PR (ms), QT (ms), QT corrected for HR (QTc) intervals (Fridericia's correction QTc (ms) = QT/RR^{1/3}), QRS duration (ms), and HR (bpm). In addition, the mean value (95% CI) at each visit will be plotted for QTc.

The number and percentage of subjects meeting the threshold analysis criterion during the TE Period of the TE Period will be summarized for selected ECG parameters based on the Safety Set. The threshold analysis criteria are provided in Appendix.

Listings will be provided for the ECG measurements.

10.6.4 Vital Signs

For vital signs measurements, raw values and change from baseline values will be summarized at each visit of the TE Period for the following parameters: systolic and diastolic blood pressure (SBP/DBP) (mmHg), temperature (°C), pulse rate (beats per minute), respiratory rate (breaths per minute), weight (kg), length/height (cm), and BMI (kg/m²).

The number and percentage of subjects with at least one potentially abnormal SBP and/or DBP during the TE Period of the TE Period will be summarized separately based on the Safety Set using threshold criteria provided in Appendix. Potentially abnormal SBP and DBP by percentile (adjusted for sex, age, and length/height) will be provided, including:

- Number and percentage of subjects in categories: $\geq 90\%$ to < 95%; $\geq 95\%$ to < 99% + 5 mmHg; $\geq 99\% + 5$ mmHg, during the TE Period
- Number and percentage of subjects with SBP and DBP percentiles ≥95% at least once and at least twice during the TE Period
- Number and percentage of subjects with SBP and DBP percentiles ≥95% at each visit in the TE Period

The length/height adjustment will be based on length/height-for-age z-scores and their corresponding percentiles using the standard normal distribution (Appendix). The length/height percentiles will be further mapped per the following rules displayed in Table 9-1:

Table 9-1 Grouped Percentiles for Length/Height-for-Age Z-scores

Calculated Percentiles (%)	Grouped Percentiles (%)

0 – <7.5	5
7.5 – <17.5	10
17.5 – <37.5	25
37.5 – <62.5	50
62.5 – <82.5	75
82.5 – <92.5	90
92.5 – 100	95

The sex- and age-adjusted normal range for SBP and DBP for each grouped length/height percentile is based on the SBP/DBP table on the National Heart, Lung, and Blood Institute (NHLBI) website (http://www.nhlbi.nih.gov/health-pro/guidelines/current/hypertension-pediatric-jnc-4/blood-pressure-tables, accessed Oct 26, 2021).

Listings of subjects with potentially abnormal SBP and/or DBP will be provided.

The mean (+/- SD) value at each visit will be plotted separately for SBP and DBP.

Listings will be provided for vital signs parameters.

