9 ANALYSIS PERIOD

The analysis periods are described below.

The **Treatment-emergent (TE) Period** will start on or after the first dose date of study drug in Study 124 to 18 days (inclusive) after the last dose date of study drug in Study 124 or up to the last day in Study 124, whichever occurs first.

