10.6.6 Pulse Oximetry

For pulse oximetry measurements, raw values and change from baseline values will be summarized at each visit of the TE Period for the percent of oxygen saturation by pulse oximetry.

The number and percentage of subjects with shift changes from baseline (normal/missing and low according to the reference range) to the lowest percent of oxygen saturation during the TE Period of the TE Period will be summarized based on the Safety Set.

Listings for pulse oximetry measurements will be included in vital signs listings.

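### The blood-pressure percentile counts in SAP 10.6.4 carry no baseline status and mean BP change is in raw mmHg, so repeated readings and growth can be misread as a drug effect

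*SAP*

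**What the plan says.** SAP 10.6.4 plans three percentile displays for systolic and diastolic pressure: counts in three bands starting at the 90th percentile; the "Number and percentage of subjects with SBP and DBP percentiles ≥95% at least once and at least twice during the TE Period"; and the "Number and percentage of subjects with SBP and DBP percentiles ≥95% at each visit in the TE Period". All three are confined to the treatment-emergent (TE) period. None has a baseline row, a shift from baseline or an expected count. The percentiles are growth-adjusted: "Potentially abnormal SBP and DBP by percentile (adjusted for sex, age, and length/height) will be provided".

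The continuous summaries are different. Raw values and change from baseline are in mmHg, and "The mean (+/- SD) value at each visit will be plotted separately for SBP and DBP", with no adjustment for age or size. Protocol 12.3.5.4 plans the same raw summaries.

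For pulse oximetry, SAP 10.6.6 does use baseline status, tabulating "shift changes from baseline (normal/missing and low according to the reference range") to the lowest on-study value.

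SAP 10.1 defines baseline as the last value on or before the first Study 124 dose. For Rollover children this comes after the 24 weeks of treatment in Study 122B (SAP 7.1).

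**The concern.** Vital signs are part of the primary endpoint, and the primary analysis is entirely descriptive. With no control arm, a table showing that a third of children had a BP at or above the 95th percentile has to be judged against something, and SAP 10.6.4 supplies nothing. A 95th percentile flags about 1 reading in 20 in the reference population by construction, and a cumulative count rises with every further reading.

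The mmHg means raise a separate problem. The children start at 12 to <24 months and are followed for 96 weeks. If BP rises with age and size over that span, the plotted mean rises whether or not the drug has any effect.

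In both cases a background pattern could be taken for a safety signal, or a real effect dismissed as background.

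**Working it through.** The documents give no expected BP count, so there is no planned figure to reproduce.

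**Visits.** Protocol Table 3-1 (Rollover): Day 15 + seven visits from Week 12 to Week 84 + Week 96 = 9. Table 3-2 (LUM/IVA-naïve): Day 15 + Weeks 4, 8, 12, 16 + six visits from Week 24 to Week 84 + Week 96 = 12. A Safety Follow-up Visit makes these 10 and 13.

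**Chance counts, independent readings.** Assume 5% exceedance per reading, which holds if the reference population applies, and one BP parameter.
- At least once: 1 − 0.95^k. For k = 9 this is 1 − 0.630 = 37.0%; for k = 12, 1 − 0.540 = 46.0%.
- At least twice: 1 − 0.95^k − k × 0.05 × 0.95^(k−1). For k = 9, 1 − 0.630 − 0.299 = 7.1%; for k = 12, 1 − 0.540 − 0.341 = 11.8%.

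**Chance counts, correlated readings.** The documents give no within-child correlation ρ, so a range is shown. Given a child effect u ~ N(0,1), the exceedance probability is p(u) = Φ((√ρ·u − 1.645)/√(1−ρ)), which averages to 5%. The binomial probabilities are averaged over u. The last two columns restrict the count to children below the 95th percentile at a single baseline reading.

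| ρ | Once, k=9 | Once, k=12 | Twice, k=9 | Twice, k=12 | Once if <95% at baseline, k=9 | Same, k=12 |
|---|---|---|---|---|---|---|
| 0 | 37.0% | 46.0% | 7.1% | 11.8% | 37.0% | 46.0% |
| 0.3 | 28.8% | 34.2% | 10.1% | 14.1% | 27.1% | 32.4% |
| 0.5 | 23.3% | 27.0% | 10.4% | 13.4% | 20.7% | 24.3% |
| 0.7 | 17.7% | 19.9% | 9.8% | 11.8% | 14.2% | 16.4% |

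Per 50 children, that is about 9 to 23 flagged at least once and 4 to 7 at least twice.

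Two results follow. Restricting to children <95% at baseline lowers the at-least-once figure by 0 to 3.5 points (17.7 − 14.2 = 3.5), so most of the inflation comes from repeated readings. The by-visit proportion does not accumulate: its expected value is 5% at every visit, or 2.5 of 50 children.

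Baseline status still separates the children. At ρ = 0.4 and k = 9, a child ≥95% at baseline has a 67.9% chance of a later flag, against 23.9% for a child below it.

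**Which readings count.** Naïve children also have two postdose readings on each of Days 1 and 15, giving 12 + 4 = 16 readings, or 17 with Safety Follow-up. If all count and are independent, at least once is 56.0% or 58.2%. Same-day readings will be correlated, so these are high. Appendix A of the SAP maps the predose Day 15 reading to the Day 15 visit, but 10.6.4 does not say which readings enter the cumulative counts. The SAP's TE window runs to "18 days (inclusive) after the last dose date of study drug in Study 124" (or the last study day if earlier), against 14 days in protocol 12.3.1. This affects whether a Safety Follow-up reading counts.

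**Growth.** 96 × 7 / 365.25 = 1.84 years. The documents give no BP slope. Assumed slopes of 0.5, 1, 2, 3 and 5 mmHg per year give drifts of 0.9, 1.8, 3.7, 5.5 and 9.2 mmHg. For scale, with 50 children and an assumed SD of change of 10 mmHg, a 95% interval has half-width 1.96 × 10/√50 = 2.8 mmHg. Growth alone would exceed this above about 2.8/1.84 = 1.5 mmHg per year. The SAP plans no such interval for BP.

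**The case against.** The strongest reply is that much of this is already covered. The by-visit ≥95% proportion is planned and does not accumulate. The at-least-twice count dampens single-reading noise. "Listings of subjects with potentially abnormal SBP and/or DBP will be provided", and all vital signs are listed, so baseline status can be recovered for about 50 children. No hypothesis is tested. The laboratory and ECG threshold counts (SAP 10.6.2 and 10.6.3) are also TE-only, and the raw mmHg summaries follow the protocol.

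Most of that is fair and limits the point. It does not remove it. The by-visit table has no baseline column, at-least-twice still flags about 7% to 14% by chance, and listings do not give an aggregate comparison. The absence of testing does not help when the descriptive counts are the primary analysis.

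A second objection concerns the obvious remedy. A shift from one baseline reading to the worst of 9 to 13 later ones compares about 5% with 18% to 49% under no drug effect, so it shows apparent worsening by itself. This stands. A shift table alone is not the answer.

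A third is that Rollover baseline is not an untreated value. Dropping Rollover children already ≥95% could hide an effect that began in Study 122B. This also stands, and argues for splitting by baseline status rather than excluding, and for reporting by cohort.

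**Conclusion.** The concern holds in a limited form. The cumulative BP counts lack a reference, and the mmHg change mixes growth with any drug effect. Under no drug effect, about 18% to 46% of children would be flagged at least once and 7% to 14% at least twice. This assumes 5% exceedance per reading, 9 to 12 visits, correlation between 0.7 and 0, and one parameter; counting either systolic or diastolic would be higher. The 0.9 to 9.2 mmHg drift depends wholly on an assumed slope.

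A reader might infer more than the documents support:
- That growth inflates the percentile counts. It does not, because they are already adjusted.
- That the missing baseline causes the high cumulative counts. It accounts for at most about 3.5 points; the number of readings is the main driver.
- That the displays will show a false drug effect. They can be misread as one; nothing in the plan commits the sponsor to that reading.
- That extra visits in naïve children bias a comparison. SAP 10.6.4 plans no comparison between cohorts.

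**What to change.** In SAP 10.6.4:

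1. Add a baseline column to the by-visit ≥95% table and make it the main BP percentile display.
2. Show the at-least-once and at-least-twice counts split by baseline status (<95% or ≥95%), with the number of readings per child and the count expected by chance over a stated range of correlation. State whether postdose, unscheduled and Safety Follow-up readings count. Do not present a baseline-to-worst shift on its own as evidence of worsening.
3. Beside raw mmHg, summarise and plot change from baseline in observed BP minus the child's sex-, age- and height-specific 95th-percentile limit. The SAP already needs that limit for its counts. The limit moves in steps between the height groups of SAP Table 9-1, so individual changes will be slightly uneven.
4. Present all of these for Rollover and LUM/IVA-naïve children separately, with a note that Rollover baseline follows treatment in Study 122B.

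This is programming only and needs no new data: a few more table columns and one more plot. Splitting about 50 children by cohort and baseline status will leave some small cells, which is acceptable in a descriptive display.

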10.6.5 Physical Examination

Listings will be provided for physical examination findings.

10.6.6 Pulse Oximetry

For pulse oximetry measurements, raw values and change from baseline values will be summarized at each visit of the TE Period for the percent of oxygen saturation by pulse oximetry.

The number and percentage of subjects with shift changes from baseline (normal/missing and low according to the reference range) to the lowest percent of oxygen saturation during the TE Period of the TE Period will be summarized based on the Safety Set.

Listings for pulse oximetry measurements will be included in vital signs listings.

10.6.7 Ophthalmological Examinations

OE findings will be presented as data listings.

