## 12.3.5.7 Ophthalmological Examinations

OE findings will be presented as a data listing.

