6 STUDY ENDPOINTS

6.1 Primary Endpoint

Safety and tolerability assessments based on adverse events (AEs), clinical laboratory (serum chemistry and hematology), standard 12-lead electrocardiograms (ECGs), vital signs, pulse oximetry, and ophthalmological examinations (OEs).

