10.6 Safety Analysis

Evaluating the safety and tolerability of long-term LUM/IVA treatment is the primary objective of this study. The safety profile of the study drug will be assessed in terms of the following safety and tolerability endpoints:

- AEs
- Clinical laboratory measurements (serum chemistry and hematology)
- Standard 12-lead ECGs
- Vital signs
- Pulse oximetry
- Physical Examinations
- OEs

Safety endpoints will be summarized descriptively based on the Safety Set.

All listings will be provided based on the All Subjects Set.

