10.6.1 Adverse Events

AEs will be classified as pretreatment AEs, treatment-emergent adverse events (TEAEs), or post-treatment AEs, defined as follows:

Pretreatment AE: Any AE that started before the first dose date of study drug in Study 124.

TEAE: Any AE that worsened (either in severity or seriousness) or that was newly developed on or after the first dose date of study drug through the end of the TE Period.

Post-treatment AE: Any AE that increased in severity or was newly developed after the TE Period.

For AEs with missing or partial start dates, if there is no clear evidence that the AEs started before or after study treatment, the AEs will be classified as TEAEs.

Details for imputing missing or partial start dates of AEs are described in Appendix.

TEAE summaries will be presented using number and percentages of subjects for the TE Period based on the Safety Set.

An overview of the TEAE profile will be provided, including total number of TEAEs, with number and percentage of subjects and for the following categories: (1) Any TEAEs; (2) Grade 3/4 TEAEs; (3) TEAEs by Strongest Relationship to the Drug; (4) TEAEs by Maximum Severity; (5) TEAEs Leading to Treatment Interruption; (6) TEAEs Leading to Treatment Discontinuation; (7) Serious TEAEs; (8) Related Serious TEAEs; (9) TEAEs Leading to Death.

AE summary tables will be presented for TEAEs only and will include the following:

- All TEAEs
- Grades 3/4 TEAEs
- TEAEs by Strongest Relationship
- TEAEs by Maximum Severity
- Related TEAEs
- TEAEs Leading to Treatment Interruption
- TEAEs Leading to Treatment Discontinuation
- Serious TEAEs
- Related Serious TEAEs
- TEAEs Leading to Death
- Frequently Reported TEAEs (≥5% at the PT level)

These summaries will be presented by MedDRA SOC and PT using frequency counts and percentages (i.e., number and percentage of subjects with any event) and exposure-adjusted number of events in 100PY. When summarizing the number of events, a subject with multiple events within a category is counted multiple times in that category. When

summarizing the number and percentage of subjects with any event, subjects with multiple occurrences of the same AE or a continuing AE will be counted once, only the maximum severity level will be presented in the severity summaries, and only the strongest relationship level will be presented in the relationship summaries.

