Additional summary table in which the frequency counts and percentages will be presented for TEAEs during the TE period for the following:

- All TEAEs by PT
- Non-Serious TEAEs by SOC and PT
- Related Non-Serious TEAEs by SOC and PT

In addition, listings containing individual subject data for all TEAEs leading to treatment interruption, TEAEs leading to treatment discontinuation, deaths, and serious adverse events (SAEs) will be provided separately for the TE Period. All AEs, including pre- and post-treatment AEs, will be presented in individual subject data listings for the TE Period.

Note that if an event increases in its severity, it will be reported as a separate event in the clinical database and thus may be counted more than once.

Analysis of AEs of Special Interest (AESI):

Three types of AESIs are proposed for Study 124; the Customized MedDRA Queries (CMQ) used may change before database lock.

1. Elevated Transaminases AESI

The AESI of elevated transaminases is defined as AEs whose PTs fall into any of the following categories:

- Alanine aminotransferase abnormal
- Alanine aminotransferase increased
- Aspartate aminotransferase abnormal
- Aspartate aminotransferase increased
- Transaminases abnormal
- Transaminases increased
- Liver function test abnormal
- Liver function test increased
- Hypertransaminasaemia
- Hepatic enzyme increased
- Hepatic enzyme abnormal
- 2. Respiratory Symptom AESI

The AESI of respiratory symptoms is defined as AEs whose PTs fall into any of the following categories:

- Chest discomfort
- Dyspnoea
- Respiration abnormal
- 3. Respiratory Event AESI (including respiratory symptoms or reactive airways)

The AESI of respiratory symptoms or reactive airways is defined as AEs whose PTs fall into any of the following categories:

- Asthma
- Bronchial hyperreactivity
- Bronchospasm
- Chest Discomfort
- Dyspnoea
- Respiration abnormal
- Wheezing

TE AESIs will be summarized using the Safety Set by:

- 1. Number and percentage of subjects by PT
- 2. Number and percentage of subjects by Maximum Severity
- 3. Descriptive summary of duration of events (days)
- 4. Descriptive summary of time-to-onset of the first event (days, relative to first dose date)
- 5. Number and percentage of subjects with exposure-adjusted number of events in 100PY for: (1) TEAEs Leading to Treatment Interruption; (2) TEAEs Leading to Treatment Discontinuation; (3) Serious TEAEs; (4) Related Serious TEAEs; and (5) TEAEs Leading to Death

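### Ophthalmological examinations are the only one of six primary-endpoint components with no planned summary: findings not recorded as AEs, and ocular AEs first dated at the Follow-up OE, enter no table, and no number examined is given

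*SAP*

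**What the plan says.** SAP 6.1 and Protocol 7.1 name six components of the primary endpoint: AEs, clinical laboratory tests, ECGs, vital signs, pulse oximetry and OEs. SAP 10.6 names OEs among the safety endpoints and states: "Safety endpoints will be summarized descriptively based on the Safety Set". The Statistical Analyses part of the protocol synopsis makes a similar commitment, with counts and percentages for categorical endpoints.

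For OEs, SAP 10.6.7 limits the output to listings: "OE findings will be presented as data listings". Protocol 12.3.5.7 does the same: "OE findings will be presented as a data listing". Physical examinations are treated alike in SAP 10.6.5 ("Listings will be provided for physical examination findings"), but they are not part of the primary endpoint.

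For AEs, SAP 10.6.1 states: "AE summary tables will be presented for TEAEs only and will include the following". A post-treatment AE is defined there as "Any AE that increased in severity or was newly developed after the TE Period". SAP Section 9 ends the TE Period no later than 18 days after the last dose. Protocol 9.1.3 schedules the Follow-up OE 24 weeks (± 14 days) after the last dose, and Protocol 13.1.1.3 extends the collection of ocular AEs to that examination. On listings, SAP 10.6.1 says: "All AEs, including pre- and post-treatment AEs, will be presented in individual subject data listings for the TE Period".

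**The concern.** Protocol 9.3.3 explains why the OEs are done. Lens opacities were seen in a juvenile-rat study; the sponsor considers them unlikely to matter in humans, and periodic OEs are meant to confirm that view. This trial is one contributor to a programme-wide effort. Supporting an absence of findings needs two numbers: how many children had a new or worsened opacity, and how many were examined. The planned tables give the first only for events recorded as AEs within the TE Period, and never give the second.

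The denominator is not a formality at this age. The protocol allows for inadequate slit-lamp examinations at screening (8.2.2, 9.1.1.1, 9.1.1.2), and the OE at early termination is waived if one was done in the preceding 12 weeks. Disposition counts cannot stand in for it, because Protocol 12.3.2.1 defines study completion by the Safety Follow-up Visit, where no OE is scheduled.

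**Working it through.** The documents give no figure to reproduce: no sample size calculation was made and no OE rate is stated. The check compares the planned outputs and then does day arithmetic.

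**1. Planned output for each component**

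| Component | SAP section | Planned summary |
|---|---|---|
| AEs | 10.6.1 | Counts, percentages and exposure-adjusted events, TEAEs only |
| Laboratory | 10.6.2 | By-visit summary, low/high counts, threshold counts |
| ECG | 10.6.3 | By-visit summary, threshold counts |
| Vital signs | 10.6.4 | By-visit summary, counts of potentially abnormal blood pressure |
| Pulse oximetry | 10.6.6 | By-visit summary, shift from baseline |
| OEs | 10.6.7 | None (listing) |

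Five of six have a summary. None of the three AEs of special interest in SAP 10.6.1 is ocular.

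**2. Can a Follow-up OE fall inside the TE Period?**

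- Follow-up OE: 24 × 7 ± 14 = 168 ± 14, so 154 to 182 days after the last dose.
- Gap after the SAP TE Period: 154 − 18 = 136 to 182 − 18 = 164 days.
- Gap after the protocol's 14-day TE Period (12.3.1): 154 − 14 = 140 to 182 − 14 = 168 days.

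No in-window Follow-up OE can fall inside the TE Period under either definition. An ocular AE first dated there is a post-treatment AE and enters no table.

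Subjects who stop early are in a similar position. Protocol 9.1.4 asks them to continue assessments through Week 96, so OEs more than 18 days after their last dose are also outside the TE Period. General AE collection has normally ended by then (Protocol 13.1.1.3), so a finding at such an OE may not be recorded as an AE at all. The documents do not say how many subjects this would affect.

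**3. Why the denominator matters**

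With zero findings in N children, the two-sided 95% exact upper limit is 1 − 0.025^(1/N):

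- N = 50 (planned total): 7.1%
- N = 40 (assumed): 8.8%
- N = 30 (assumed): 11.6%

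The smaller N values are illustrations, because no dropout or missed-examination rate is given. The same zero carries different information depending on an N that no planned table reports.

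**4. Appendix A rows that matter once OEs are tabulated by visit**

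- The OE Follow-up Visit row has target Day 687. Week 96 is Day 673 and the last dose is taken before that visit, about Day 672. A completer's Follow-up OE is then due at 672 + 168 = Day 840 (826 to 854), which is 840 − 687 = 153 days after the stated target.
- The Week 96 OE window closes at Day 680. Tables 3-1 and 3-2 allow the OE within 2 weeks of the scheduled visit. Counted from the target day, that reaches 673 + 14 = Day 687. Counted from an actual visit at its latest in-window day, 673 + 7 = 680, it reaches 680 + 14 = Day 694. So 7 or 14 permitted days map to no windowed visit.

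**The case against.** The best case for the plan is that this is a choice between a table and a listing. Protocol and SAP agree on a listing, so nothing was dropped. The study is single-arm and descriptive, with about 50 subjects and no hypothesis testing, and a reader could count from the listing. Clinically significant worsening on a study assessment becomes an AE under Protocol 13.1.1.2 (OEs are not named there, but the list is open), and on-treatment ocular AEs then enter the SOC/PT tables. Restricting AE tables to the TE Period is a general rule, not one aimed at OEs.

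All of that stands, and it limits the point. It does not answer the conflict between SAP 10.6 and 10.6.7, the missing denominator, or the absence from any table of events that the protocol makes a special exception to collect. Counting by hand also leaves new, worsened and examined to be defined after the data are seen.

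Three stronger readings are tempting, and the documents do not support them.

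- A reader might infer that lens findings are lost or that late ocular AEs vanish. They do not: SAP 10.1 requires all individual data to be listed and SAP 10.6 bases all listings on the All Subjects Set. The restriction to the TE Period in the AE-listing sentence contradicts itself and is absent from Protocol 12.3.5.1, so it is best read as a drafting slip.
- A reader might infer that ocular AEs are never tabulated. Those with onset in the TE Period are, as are those with missing or partial dates that Appendix C places there.
- A reader might treat every OE without a by-visit summary as a missed finding. Most may be normal, and the number of scheduled OEs says nothing about the number of findings.

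A fair objection to the remedy is that the Rollover baseline follows 24 weeks of Study 122B treatment, so an opacity that arose in that study would count as baseline. Children who move to commercial LUM/IVA also still have the Follow-up OE, so a single pooled row would mix treated and untreated children. The table has to show this.

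**Conclusion.** The point holds as a reporting gap in one primary-endpoint component. One of six components has no planned summary, and two groups of findings enter no table. Ocular AEs first dated at the Follow-up OE arise at least 136 days too late for the TEAE tables. The number of findings affected cannot be estimated from the documents and may be zero.

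This rests on the SAP and protocol outputs alone. The IDMC Analysis Plan is not among the documents, so counts seen by the IDMC cannot be ruled out. The change is worth making before the data cut. It does not call data collection or the conduct of the trial into question. The difference in TE Period length (14 days in the protocol, 18 in the SAP) is a separate matter: the gap exists under either.

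**What to change.** - **SAP 10.6.7:** add one descriptive Safety Set table giving, at each OE and at any time, the number examined and the n/N with a new or worsened lens opacity or cataract relative to the Study 124 baseline OE. Show the Follow-up OE separately from the others. Show Rollover and LUM/IVA-naïve subjects separately, or footnote that the Rollover baseline follows 24 weeks of treatment. Flag subjects known to have moved to commercial drug; a complete split may not be possible, because medications are recorded only through the Safety Follow-up Visit (Protocol 9.5).
- **Ocular AEs:** tabulate them through the Follow-up OE regardless of the TE window.
- **SAP 10.6.1:** delete the closing restriction to the TE Period from the all-AE listing sentence, so that it agrees with Protocol 12.3.5.1 and SAP 10.1.
- **SAP Appendix A:** relabel the OE Follow-up Visit row as the Follow-up OE, 24 weeks after the last dose, assigned by nominal visit. Assign the Week 96 OE by nominal visit as well, or extend its window to cover the full protocol allowance (Day 687 or Day 694, depending on how the 2 weeks are counted).

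The cost is SAP wording and two small tables from data already collected. If the eCRF does not code findings as new or worsened, those in about 50 subjects must be classified before lock. The downside is small cells, and late ocular events that may be unrelated to study drug will appear in a table.
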